SEM	Standard Error of the Mean
SM	Starting Materials
SOFA	Sequential Organ Failure Assessment
SUSAR	Serious Unexpected Adverse Reaction
TK	Toxicokinetic(s)
WHO	World Health Organization

PROTOCOL SYNOPSIS

Title: Phase I/IIa Study of Descartes-30 in Acute Respiratory Distress Syndrome.
Study Description: This is a Phase I/IIa, open-label, emergency study to test the safety of Descartes-30 cells in patients with acute respiratory distress syndrome (ARDS) and severe pneumonia (PNA). The cell product consists of Mesenchymal Stem Cells (MSCs) engineered to express DNase1 and DNase1L3 to degrade Neutrophil Extracellular Traps (NETs), which are a cardinal and causative feature of ARDS. In the dose escalation arm (Arm 1), the study will enroll three patients with ARDS into each of four successive dose levels to test escalating doses of Descartes-30. An additional 12 patients with ARDS (ARDS Cohort) and 12 patients with severe pneumonia (PNA Cohort) will be enrolled into a dose expansion arm (Arm 2).
Objectives: **The primary objective** is to assess the safety of Descartes-30 in patients with moderate-to-severe ARDS. Safety will be determined principally by assessment of adverse events (AEs) and serious adverse events (SAEs).
[REDACTED]

The exploratory objectives are:
[REDACTED]

Endpoints: The primary endpoint is the Maximum Tolerated Dose (MTD) defined as the highest Dose Level at which no more than one patient has shown Dose-Limiting Toxicity (DLT).
[REDACTED]

Study Population:

The study will enroll about 36 patients: about 12 patients in a dose escalation arm and about 24 patients in an expansion arm. The major eligibility criteria are as follows: (1) 18 years or older; (2) respiratory failure; (3) ARDS diagnosis per Berlin criteria within 14 days of first cell infusion OR severe PNA per ATS/IATS criteria within 7 days of first cell infusion; (4) maximal medical therapy already in place, in the opinion of the treating physician; (5) informed consent from participant or health care proxy. Patients will be excluded if they (1) are moribund with expected survival <24 hours, (2) are pregnant (3) have severe baseline morbidity prior to diagnosis of ARDS or PNA, (4) have used Pulmozyme® (dornase alfa) after diagnosis of ARDS or PNA. For complete list of inclusion and exclusion criteria, see Full Protocol.

Phase:

I/IIa

Study Site:

Multi-center

Study Design:

Patients diagnosed with ARDS or PNA will undergo screening during which informed consent will be obtained and eligibility assessed. Up to 7 or 14 days may elapse between confirmation of PNA or ARDS diagnosis respectively and administration of the first infusion of study product. Patients will be dosed once per day for 3 consecutive days (Day 0, 1, 2). In Arm 1 (Dose Escalation), patients were monitored for 7 days after the first Descartes-30 infusion (unless they are discharged from the administering unit prior to Day 7) with a safety review on Day 7 (or last day in the administering unit, whichever comes earlier) to determine whether the next patient in the trial can be dosed. In Arm 2 (Dose Expansion), patients will be enrolled consecutively to receive treatment on Day 0, 1, and 2 at a dose up to the MTD determined in Arm 1. For both Arms, there will be an optional visit on Days 14 and 21 and a mandatory visit on Day 28. Long-term follow-up will occur at Day 90 (in-person or telephone contact).

Study Intervention:

The study product will be manufactured from qualified allogeneic donors under GMP standards. After the product passes Quality Control, it will be shipped to the study site for storage. Patients will receive the first dose of Descartes-30 cells via intravenous administration within 14 days of diagnosis of ARDS or within 7 days of diagnosis of PNA. Patients will receive two more infusions over the following 2 days unless they meet the criteria for holding dose or discontinuing study treatment.

In the dose escalation arm (Arm 1), the following doses of Descartes-30 cells are planned:

- Dose Level 1: 100 million cells administered on Days 0, 1 and 2
- Dose Level 2: 300 million cells administered on Days 0, 1 and 2
- Dose Level 3: 600 million cells administered on Days 0, 1 and 2

- Dose Level 4: 1200 million cells administered on Days 0, 1 and 2

An additional 12 patients per cohort (ARDS or PNA) may be enrolled at a dose up to MTD.

Study Duration: 30 months

Participant Duration: 3 months

1 SCHEDULE OF ACTIVITIES (SOA)

Procedures	Screening Visit ^j		Study Product Infusion Day 0		Study Product Infusion Day 1		Study Product Infusion Day 2		Safety Monitoring Day 3-6 ^{k,l}		Primary safety review Day 7 or last day in administering unit ^w		Short-term Follow-up Day 14 ^l		Short-term Follow-up Day 21 ^l		Short-term Follow-up Day 28 or last day in hospital ^m		Long-term Follow-up Day 90+ 14 ⁿ	
Informed consent	X																			
Demographics	X																			
Medical history	X																			
Physical examination ^a	X	X	X	X	X	X	X	X	X ^{s,t}	X ^{s,t}	X ^{s,t}								X	
Height and weight	X																			
Concomitant Medications	X	X	X	X	X	X	X	X	X	X	X	X	X	X	X	X	X	X		
Descartes-30 Cell Infusion		X	X	X	X															
Clinical Endpoint Assessment ^b	X	X	X	X	X	X	X	X	X	X	X	X	X	X	X	X	X	X		
Vital signs ^c	X	X	X	X	X	X	X	X	X ^s	X ^s	X ^s	X ^s	X ^s	X ^s	X ^s	X ^s	X ^s	X		
CBC with differential ^d	X	X ^v	X ^v	X ^v	X ^v	X ^v	X ^v	X ^v	X ^s	X ^s	X ^s	X ^s	X ^s	X ^s	X ^s	X ^s	X ^s			
Serum chemistry ^{d, e}	X	X ^v	X ^v	X ^v	X ^v	X ^v	X ^v	X ^v	X ^s	X ^s	X ^s	X ^s	X ^s	X ^s	X ^s	X ^s	X ^s			
CRP, ferritin, D-Dimer ^d		X	X	X	X	X	X	X												
Blood and/or sputum culture ^x	X																			
COVID-19 nucleic acid test ^f	X																			
Urinalysis ^d	X	X ^v	X ^v	X ^v	X ^v	X ^v	X ^v	X ^v	X ^s	X ^s	X ^s	X ^s	X ^s	X ^s	X ^s	X ^s	X ^s			
Pregnancy test ^g	X																			
ECG		X ^s	X ^s	X ^s																
Research Blood Collection ^h	X	X ^r	X	X ^r	X ^p	X	X ^{s,t}	X ^{s,t}	X ^{s,t}	X ^{s,t}	X ^{s,t}									
PT/INR, PTT		X ^r	X	X ^r	X ^p															
Exploratory BAL ^{h,o}	X					X ^p														
Chest X-Ray or Chest CT		X ^p		X ^p		X ^p	X ^{q,u}	X ^s	X ^s	X ^s	X ^{s,q}									
AE review and evaluation	X	X	X	X	X	X	X	X	X	X	X	X	X	X	X	X	X	X	X	
APACHE II score	X ⁱ																			

- a See Section 6 for details of physical exam at each visit.
- b Clinical End-Point Assessments include: Survival (Y/N), On mechanical ventilation (Y/N), In ICU (Y/N), In Hospital (Y/N), Use of anticoagulation (drug, dose, intent: prophylaxis vs therapeutic), WHO Ordinal Score. Following parameters to be collected only if patient is still in ICU: Sequential Organ Failure Assessment (SOFA), $\text{PaO}_2/\text{FiO}_2$, ventilation variables (See Section 6 for details), recording of vasoactive drugs and renal support, recording of supportive interventions that can impact clinical endpoints (i.e., use of prone ventilation, use of paralytics, use of pulmonary vasodilators, use of corticosteroids, use of oral decontamination and raising the head of the patient to at least 30° to prevent ventilator-associated pneumonia).
- c Vital signs include core temperature, mean arterial pressure (mmHg), pulse (beats/min), respiratory rate (breaths/min).
- d Samples should be taken in the morning between 04:00 and 10:00 using the values closest to 10:00.
- e Serum Chemistry includes Glucose, Ca, Mg, Phos, ALP, Albumin, Total Protein, Total Bilirubin, K, Na, Cl, HCO₃, BUN, Cr, ALT, AST, LDH, Amylase.
- f Only if there is clinical suspicion for COVID-19.
- g Blood or urine test, only in women of childbearing potential.
- h See Laboratory Manual for details of sample collection for exploratory assays.
- i See [Appendix A](#) for APACHE II score system.
- j Patient should continue to have respiratory failure as defined in Section 5.1 and moderate/severe ARDS status at least for 24 hours prior to signing consent. Screen visit and Day 0 infusion can be on the same day.
- k Assessments below should be done once a day unless stated otherwise.
- l If patient is discharged from the hospital these assessments can be omitted.
- m These assessments will be done on the day the patient leaves the administering unit or on Day 28, whichever comes earlier.
- n In-person or telemedicine. Omit Research Blood collection if telemedicine.
- o Optional based on PI discretion. If not possible, use tracheal aspirates for intubated patients and induced (preferred) or expectorated sputum for patients who are not intubated.
- p At least one time only during this period
- q If possible, CT scan is preferred.
- r Collection is done one-time pre-infusion and one-time post-infusion. See Laboratory Manual for details (for Research blood collections).
- s Should be done only if patient is in the hospital and procedure is Standard of Care as per PI discretion.
- t If patient is still in the administering unit.
- u Imaging within 24h before or after visit will be accepted.
- v Mandatory in Arm 1 and done only if SOC at institution in Arm 2.
- w Administering unit is ICU in Arm 1 (Dose Escalation) and ARDS Cohort of Arm 2 (Dose Expansion), and ICU, IMC, or acute care floor in the PNA Cohort of Arm 2.
- x Blood and/or sputum culture should be collected prior to administration of antibiotics. Cultures collected during admission prior to screening are accepted.

2 INTRODUCTION AND RATIONALE

Descartes-30 is a cell therapy product consisting of allogeneic human Mesenchymal Stem Cells (MSCs) engineered with mRNA to transiently secrete recombinant human Dnase1 and recombinant human Dnase1L3. These enzymes are naturally secreted by human cells and are an important homeostatic tool to break down extracellular DNA and chromatin to control inflammation.^{23,24} Both enzymes have potent activity in breaking down neutrophil extracellular traps (NETs), long strands of DNA and chromatin generated by neutrophils during acute inflammation in a programmed cell death process known as NETosis.⁹ NETs exacerbate inflammation by trapping immune cells, and NET breakdown inhibits inflammation.⁹ NETs are present in acute respiratory distress syndrome (ARDS) and play a key role in the disease process.^{14,22}

Clinical data strongly suggests that allogeneic human MSCs can home to the lungs, inhibit inflammation, and improve symptoms in patients with ARDS.³⁹⁻⁴² Breakdown of NETs by Dnases is also expected to reduce inflammation and improve symptoms in ARDS.⁹ Descartes-30 combines the inherent immunosuppressive capacity of MSCs with the potent and synergistic capacity of Dnase1 and Dnase1L3 to break down NETs and promote healing of tissue damage. The enzymes are expected to work quickly and synergistically within the diseased tissue. The benefit: risk ratio is enhanced by transient and local secretion of the enzymes for this acute condition.

There are no FDA-approved treatments for ARDS, and its management is based entirely on supportive care and treatment of the underlying clinical insult. Because ARDS is a host reaction to the insult, such treatments do not address ARDS mechanisms *per se*, and there is a need for treatments that do. Neutrophil activation is critical to the pathogenesis of ARDS, and ample evidence exists to implicate NETosis^{10,15,31}, leading to generation of thick, viscous NETs that directly propagate inflammation. Pulmonary parenchyma NET levels correlate with disease severity.¹⁸⁻²⁰ An ideal treatment for ARDS would reduce neutrophil activation while removing excess NETs. Descartes-30 can potentially achieve both objectives as MSCs are known to exhibit anti-inflammatory properties in the context of ARDS, and the MSCs have been specifically modified to secrete Dnases to degrade NETs. Therefore Descartes-30 is expected to dramatically improve outcomes in ARDS without eliciting significant adverse events.

Increased NET production has also been implicated in severe pneumonia of both bacterial and viral etiology. In bacterial pneumonia, NETs may assist dissemination of *Streptococcus pneumoniae* through cleavage of host immune proteins and inducing lung injury,²³ and foster formation of *Staphylococcus aureus* and *Pseudomonas aeruginosa* biofilms.²³⁻²⁵ Neutrophil dysfunction and NETosis have also been demonstrated in viral pneumonia, in both animal models and clinical samples of patients with influenza, varicella, and SARS-CoV-2 pneumonia.²⁶⁻²⁹ Neutrophils of patients with COVID-19 and influenza pneumonia produce higher levels of NETs inducing lung epithelial cell death,^{28,29} while in varicella-zoster virus infection the release of NETs caused by the virus was associated with dysregulated expression of alveolar epithelial cell tight junction proteins, contributing to disease severity.²⁷ Treatment of severe pneumonia has so far been limited to pathogen-targeting antimicrobials, without addressing host factors such as increased NETosis.²⁴ Notably, targeting NETs directly is not expected to interfere with other neutrophil functions important for controlling pathogens, thereby limiting risk for worsening infection.³⁰

2.1 RISK/BENEFIT ASSESSMENT

Descartes-30 consists of allogeneic human MSCs modified by introduction of mRNA to transiently secrete recombinant human Dnase1 and human Dnase1L3. Allogeneic human MSCs for therapeutic use have been well characterized and are currently administered in over 100 COVID-19-related clinical trials. Both Dnase1 and Dnase1L3 are normally expressed and found in the plasma of healthy persons. In the extracellular milieu, they do not appear to have any endogenous target except for extracellular DNA. Furthermore, both Dnase1 and Dnase1L3 are macromolecules of sufficient bulk that they do not cross the plasma and nuclear membrane of healthy cells.

Recombinant human Dnase1 has an excellent safety profile and was approved by the FDA nearly 30 years ago for inhaled administration in the treatment of cystic fibrosis (i.e., PULMOZYME®). Descartes-30 cells are engineered with mRNA that cannot modify the cell genome, eliminating the risk of gene transfer-induced transformation. No viral particles or antibiotics are used in manufacturing. The final product is confirmed to be free of residual DNA, further reducing the risk of integration. The Dnases are secreted temporarily, and their expression wanes over several days, which is expected to avoid the risk of long-term toxicity.

Because Dnases have very short half-lives in human serum, a cell-based therapy is an ideal delivery system that bypasses the need for frequent drug administration to achieve therapeutic levels of exposure. Furthermore, as MSCs naturally home to pulmonary vascular sites, Descartes-30 cells are expected to travel to the sites of NET formation that underlie ARDS and PNA, conferring spatially targeted delivery. The natural immunomodulatory properties of MSCs can further inhibit ARDS and PNA-related inflammation⁵⁸. Thus, targeted systemic delivery of Dnase-producing MSCs can benefit patients with ARDS and PNA through several mechanisms:

1. decrease airway mucus viscosity through breaking down extracellular DNA, thus improving airway clearance;
2. decrease/prevent microvascular thrombus, thus improving oxygenation;
3. reduce local tissue exposure to immune-mediated injury caused by NETs; and
4. inhibit inflammation directly by MSCs.

3 OBJECTIVES

The **primary objective** is to assess the safety of Descartes-30 in patients with ARDS. For purposes of this study, safety assessment consists of descriptive statistics and qualitative analysis of adverse events, serious adverse events, and clinical assessments shown in the schedule of assessments.

[figure not shown]
[REDACTED]

Research Samples will be collected for the following objectives:

1. [REDACTED]
- [REDACTED]
- [REDACTED]
- [REDACTED]

4 STUDY DESIGN

4.1 SCHEMA

* If not discharged from the administering unit (ICU or IMC for ARDS Cohort; ICU, IMC, or acute care floor for PNA Cohort)

Day 7 or Day of discharge from the administering unit, whichever comes first

** If not discharged from the hospital

*** Day 28 or Day of discharge from hospital, whichever comes first

\$ In-person or telephone visit

4.2 OVERALL STUDY DESIGN

This is an open-label, multi-center, Phase I/IIa study to evaluate the safety and tolerability of Descartes-30, allogeneic Mesenchymal Stem Cells (MSCs) modified to secrete recombinant human Dnase1 and recombinant human Dnase1L3 in patients with ARDS and PNA. The study will enroll about 33 patients: about 12 patients in a dose escalation arm (Arm 1) and about 12 patients in each cohort (ARDS and PNA) of an expansion arm (Arm 2). The study will involve four planned Dose Levels. An expansion arm (Arm 2) will dose up to 24 additional patients with a dose deemed to be safe in Arm 1 for additional characterization of Descartes-30 risk/benefit in ARDS and PNA. Patients in the dose escalation arm (Arm 1) will be enrolled in staggered fashion to allow adequate safety monitoring period in between patients.

For both arms, patients who are diagnosed with ARDS of any severity as per Berlin Criteria⁵ ([Appendix C](#)) will be screened and enrolled into the next available slot in the ARDS Cohort. In Arm 2, patients with radiographically confirmed PNA requiring inpatient hospitalization will be screened and enrolled into the PNA Cohort. The total dose will be split into three days and the first dose should be given within 14 days of ARDS diagnosis. Safety is monitored daily for up to 7 days while patient is in the administering unit (ICU or IMC for ARDS Cohort, ICU, IMC, or acute care floor for PNA Cohort), with a primary safety review on Day 7 or last day of stay in administering unit, whichever comes earlier. After Day 7, patients will be assessed on Day 14, 21 and 28 if they are still in the administering unit for a follow-up visit. There will be one more contact on Day 90 for long-term follow-up. This visit can be in-person or via telemedicine.

4.3 JUSTIFICATION FOR DOSE

Patients will be treated with dosing schedules outlined in Table 1.

Table 1. Definition of Dose Levels

Dose Level	Dose	Schedule ^a	Total (Cumulative) Descartes-30 dose ^b
Level 1	100 million	Days 0, 1 and 2	0.3×10^9 Descartes-30 cells
Level 2	300 million	Days 0, 1 and 2	0.9×10^9 Descartes-30 cells
Level 3	600 million	Days 0,1 and 2	1.8×10^9 Descartes-30 cells
Level 4	1200 million	Days 0, 1 and 2	3.6×10^9 Descartes-30 cells

a See Section 7.1.2.2 for criteria of delaying cell infusion or Section 7.1.2.4 for discontinuing treatment.

b The clinical dose is $\pm 20\%$ of target dose defined as the absolute number of viable MSCs.

The safe and appropriate starting dose, 100 million MSCs administered once per day for 3 days, was established based on clinical experience with MSCs in ARDS and other cardiopulmonary diseases^{43,44,47,48}. No deterioration of hemodynamic parameters was observed after infusion of up to 900 million MSCs.⁴³ Human Dnase 1 and Dnase1L3 secreted from cells are not expected to significantly alter the safety profile, as these are fully human proteins that are normally secreted and present in human blood. Their targets—extracellular chromatin/DNA—have no known physiological role except for NET formation, and therefore are not present except in pathological states. Except for the desired action of NET removal, Dnase1 and Dnase1L3 are not expected to exert any significant physiological or toxic effects.

Semi-log dose escalation between dose levels is customary for ascending dose studies, including studies with MSCs.

4.4 DOSE ESCALATION RULES

A minimum of three patients will be dosed at each dose level. In the dose escalation arm, there will be a minimum of 7 days between each patient's first cell infusion. At the time a patient is diagnosed with ARDS, the clinic will contact the sponsor who, by default, will assign the patient to the next slot in the active dose level. Patients will receive three doses of Descartes-30 cells on Days 0,1 and 2. On Day 7 or last day in ICU, whichever comes earlier, the Principal Investigator will review the clinical data with the Medical Monitor and authorize the next patient's infusion if there is no safety concern. The selection of Day 7 for safety review is based upon preclinical data demonstrating that Dnase expression wanes over 7 days. Furthermore, the study will not proceed to the next dose level until: 1) at least 3 patients in the previous dose level have been observed through Primary Safety Review; 2) no study stopping rules have been triggered; and 3) the medical safety monitor has reviewed the cumulative safety data and concluded and documented that the next Dose Level may be initiated.

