4.5 DOSE ESCALATION STOPPING RULES

The Medical Monitor will apply the following rules to determine if it is safe to proceed to the next Dose Level, or if dose escalation should stop. Pre-specified rules for pausing or stopping the whole study are described in Section 8.5 and rules for individual patient withdrawal are described in Section 8.4.

Should one of three patients in a Dose Level experience dose-limiting toxicity (DLT, see Section 8.1.2 for definition) within 7 days after receiving the first dose of the cells that is considered probably or definitely related to Descartes-30, 3 more patients will be enrolled and treated at that Dose Level. If only 1/6 of patients at that Dose Level has a DLT, and if the medical monitor agrees, treatment will proceed to the next higher Dose Level. If 2 or more out of 3 to 6 patients develop a DLT, no further patients will be dosed at that dose level. The MTD will be defined as the highest dose at which a maximum of 1 of 6 patients has a DLT. In Arm 2, up to 12 more patients who meet the eligibility criteria may be treated in each cohort (ARDS and PNA) at a dose up to MTD, provided that the medical monitor approves the enrollment of each such patient based on ongoing review of the cumulative safety data.

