7.1.2 DOSING AND ADMINISTRATION

7.1.2.1 PRE-INFUSION MONITORING AND DELAY OF CELL INFUSION

[figure not shown]
Infusions can be delayed up to 96 hours based on PI discretion. Prior to all Descartes-30 infusions, patients should be observed for 2 hours (\pm 30 min) to document their stability by meeting the following parameters and based on PI's best clinical judgement:

1. Patient is not requiring a change in ventilator settings
2. Stable use of vasopressors if the patient required vasopressors for blood pressure support.
Stable use is defined as increasing no more than 50% of baseline recorded at initiation of monitoring.

During 2-hour monitoring, following parameters should be recorded at least every 30 min: ventilation variables [type of ventilation (CPAP, BiPAP, or intubation), ventilation rate, pulse, tidal volume, positive end-expiratory pressure (PEEP)], recording of vasoactive drugs and renal support and vital signs [include core temperature, mean arterial pressure (mmHg), pulse (beats/min), respiratory rate (breaths/min)]. If patients do not meet stability criteria for 2 hours, infusion can be delayed for up to 96 hours. If infusion is delayed, the patient will be periodically monitored to assess stability. If infusion is delayed more than 96 hours due to medical instability, patients will come off study treatment. Infusions can also be delayed up to 96 hours in case of a holiday or by PI's discretion.

Patients experiencing toxicities that are probably or definitely related to Descartes-30 will have their next Descartes-30 dose delayed until these toxicities have resolved to at least Grade 2, unless in the documented opinion of the site Principal Investigator and the medical monitor it is reasonable to proceed. During this period, patients will be assessed to record adverse events and decide whether the patient meets criteria for cell infusion. The discussions between the Medical Monitor and site Principal Investigator will be documented. If a dose is delayed for more than 96 hours, the patient will come off study treatment.

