7.1.2.5 CRITERIA FOR COMING OFF-TREATMENT

Off-treatment criteria mainly apply to eligibility for repeat Descartes-30 treatments. Patients will be taken off treatment for the following:

- DLT as defined in Section 8.1.2 directly attributable to Descartes-30 cells.
- General or specific changes in the patient's condition rendering the patient ineligible for further treatment in the judgment of the investigator.

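### The escalation count and the MTD rule set no minimum exposure, so a patient who stops early without a related DLT can help clear a dose level that was only partly received

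*Combined protocol and SAP*

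**What the plan says.** **What a Dose Level is.** Table 1 in Section 4.3 defines each level by a per-infusion dose, a schedule of Days 0, 1 and 2, and a column headed "Total (Cumulative) Descartes-30 dose". A footnote on that column gives a tolerance of ±20%.

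**What clears a level.** Section 4.4 states "A minimum of three patients will be dosed at each dose level" and makes escalation conditional on three things: that "at least 3 patients in the previous dose level have been observed through Primary Safety Review", that no study stopping rule has been triggered, and that the medical monitor has documented agreement. The Primary Safety Review is on Day 7 or the last day in the unit if earlier (Sections 4.4 and 6.4), whatever was infused.

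**What the MTD is.** Section 4.5: "The MTD will be defined as the highest dose at which a maximum of 1 of 6 patients has a DLT". For escalation, that section counts DLTs within 7 days of the first dose that are probably or definitely related. The synopsis definition of the primary endpoint has no exposure condition either, and Section 9.2 refers back to Section 4.4.

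**How a course can end early.** Section 7.1.2.1: "If infusion is delayed more than 96 hours due to medical instability, patients will come off study treatment". Section 7.1.2.5 adds: "General or specific changes in the patient's condition rendering the patient ineligible for further treatment in the judgment of the investigator". Section 8.4 lists only voluntary withdrawal and death as reasons for leaving the study, so a patient who is off treatment remains under observation.

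**The concern.** The unit being tested is a three-infusion course, but the unit being counted is a patient who was dosed and reached the review. The readable text has no DLT-evaluable set, no minimum number of infusions and no replacement rule. Section 5.3 removes only patients who never received cells.

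A patient who stops for disease-related reasons has had fewer chances to show toxicity from repeated dosing, yet can count as a full non-DLT observation. The error runs in one direction, towards clearing the level. The MTD is the primary endpoint, and up to 24 Arm 2 patients may be dosed up to it.

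**Working it through.** **1. Table 1 reproduced.** Cumulative dose = 3 × per-infusion dose.

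| Level | Per infusion (million) | 3 × dose (×10^9) | Table 1 (×10^9) | After one infusion (×10^9) | After two (×10^9) |
|---|---|---|---|---|---|
| 1 | 100 | 0.3 | 0.3 | 0.1 | 0.2 |
| 2 | 300 | 0.9 | 0.9 | 0.3 | 0.6 |
| 3 | 600 | 1.8 | 1.8 | 0.6 | 1.2 |
| 4 | 1200 | 3.6 | 3.6 | 1.2 | 2.4 |

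The table is arithmetically correct. One infusion is 67% below the level's cumulative dose and two are 33% below. Both are outside the ±20% tolerance.

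**2. The rule applied literally.** Take a patient who has infusion 1, becomes unstable from the underlying disease, passes the 96-hour limit and comes off treatment. The patient was dosed, has no related DLT, is still on study and reaches the review. Condition 1 of Section 4.4 and the 0/3 or 1/6 count in Section 4.5 are met exactly as they would be by a patient who completed.

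**3. Illustrative effect on clearing a level.** The documents give no DLT rate, so the full-course risk p is an assumption, ranged from 0.20 to 0.50. Under Section 4.5,

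P(clear) = P(0 of 3) + P(1 of 3) × P(0 of next 3).

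All complete, p = 0.30: 0.343 + 0.441 × 0.343 = 0.494.

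Now let one patient in each three stop after one infusion. With equal, independent risk per infusion, that patient's risk is q = 1 − 0.70^(1/3) = 0.112.
- P(0 of 3) = 0.888 × 0.49 = 0.435
- P(1 of 3) = 0.112 × 0.49 + 0.888 × 0.42 = 0.428
- P(clear) = 0.435 + 0.428 × 0.435 = 0.621

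| Assumed p | All complete | One of each three stops after one infusion |
|---|---|---|
| 0.20 | 0.709 | 0.798 |
| 0.30 | 0.494 | 0.621 |
| 0.40 | 0.309 | 0.444 |
| 0.50 | 0.172 | 0.287 |

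Sensitivity at p = 0.30:
- If only the first three patients include an early stop, the figure is 0.582.
- If the stop comes after two infusions, q = 1 − 0.70^(2/3) = 0.212. Then P(0) = 0.386, P(1) = 0.435, and P(clear) = 0.386 + 0.435 × 0.386 = 0.554.
- If toxicity appears only with accumulation (q = 0), it is 0.696.
- If all the risk lies in the first infusion (q = p), it stays at 0.494 and there is no bias.

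**4. Information in a clean level.** With no DLT, the exact one-sided 95% upper bound on full-course risk is 1 − 0.05^(1/n): 63% with three complete patients, 78% with two.

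**5. The window.** The escalation rule's 7 days run from the first dose. Reading the 96-hour allowance in Section 7.1.2.1 as applying to each infusion, infusion 2 can fall at Day 1 + 4 = Day 5, and infusion 3 at Day 6 + 4 = Day 10. Even a completed course can therefore pass the Day 7 review before its last infusion.

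**The case against.** The strongest reply is that the plan already has a safeguard. Section 4.4 also states "Patients will receive three doses of Descartes-30 cells on Days 0,1 and 2", three is a minimum, and the medical monitor must review cumulative data and document agreement before each new level. That is real, and the monitor could discount a partial course. But it is discretion: no rule tells the monitor to do so. The synopsis also makes the later infusions conditional: "Patients will receive two more infusions over the following 2 days unless they meet the criteria for holding dose or discontinuing study treatment".

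Secondly, Section 7.2.2 expects toxicity within several hours of infusion, and the reactions listed in Section 8.1.2 have a 4-hour window. A one-infusion patient therefore informs the main expected risk. This stands, and it limits the point to the repeated schedule. Some early deteriorations would themselves be DLTs under Section 8.1.2, which sets no relatedness condition for the listed reactions. Section 4.5 does set one, so the two passages need reconciling.

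Four stronger readings are not supported.
- *The plan says partial courses count, or forecasts them.* It does neither: it permits early stops and is silent on how to count them. Section 7.1.2.5 covers only changes that make the patient ineligible for further treatment.
- *The MTD would be set at a dose nobody received.* The shortfall applies only to the patients who stopped; the others at that level had the full course.
- *A death from ARDS after one infusion clears the level.* The documents do not say whether such a patient was observed through the review.
- *The chance of an early stop is the chance of a wrong MTD.* At assumed early-stop rates of 10% to 30%, at least one of three patients stops with probability 1 − 0.9^3 = 27% to 1 − 0.7^3 = 66%. That measures how often the question arises, not how often the MTD is wrong.

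**Conclusion.** The point holds as a gap in the counting rule: as written, the escalation count and the MTD can include patients who received one or two thirds of the level's cumulative dose, with only discretionary review against it. The bias is towards escalation and concerns tolerability of the repeated, cumulative schedule, not acute per-infusion reactions.

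Its size cannot be fixed from the documents. At an assumed 30% full-course risk, with one in three stopping after one infusion, the chance of clearing rises by about 0.13 under equal risk per infusion; the extremes are no change and about 0.20. The calculation takes early stopping as unrelated to toxicity. The gap should be fixed because it bears on the primary endpoint, but the monitor's review and the per-infusion testing keep it short of a must-fix.

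**What to change.** In Section 4.4 condition 1 and Section 4.5, base the escalation count and the MTD on a pre-specified DLT-evaluable set:
- patients with a DLT after any infusion; or
- patients who received the Table 1 course within its stated tolerance and were observed through a DLT window that also covers the period after their last infusion.

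The sponsor must reconcile the 7-day window from first dose and the Day 7 review with the permitted 96-hour delays. Requiring three infusions without doing so would still admit patients not observed after the third.

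Replace non-evaluable patients for the escalation count only, and keep them in all safety tables. Have the medical monitor review each early stop for possible product relatedness; otherwise replacement could drop toxicity that was misattributed to ARDS. Report the MTD with the number of patients at each level who had one, two and three infusions.

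**Cost.** Protocol wording, slower escalation because Arm 1 enrolment is staggered by at least 7 days, and some replacements. For 12 evaluable patients, 12/(1 − d) gives 12/0.9 = 13.3, so 14 dosed at an assumed 10% early-stop rate, and 12/0.7 = 17.1, so 18 at 30%.

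One synopsis sentence describes Arm 1 monitoring in the past tense. If Arm 1 is already complete, report infusions received by level and confirm that the MTD rests on evaluable patients before relying on it in Arm 2.
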